### **15.3 Trial samples**

**All trial participants:** All trial participants will be asked to provide blood samples at baseline - a full blood count and vitamin D levels will be measured for each participant - the volume of blood taken will be no more than 10ml. At 12 months a full blood count will be measured for around 150 participants - the volume of blood taken will be no more than 4ml.

**Immunology:** For a sample of around 100 trial participants some additional immunology work (detailed in section 5.1) will be done and an additional blood sample will be taken at baseline and up to 12 months – the volume of blood taken will be no more than 6ml at each timepoint. The sample will be taken at the same time as the other blood samples.

**Flu vaccine response sub-study:** A sub-set of patients will be asked to provide a blood sample on the day of (or up to 10 days prior to this), and four weeks (28 days) after they receive their routine seasonal influenza vaccination. For those agreeing to take part in this flu vaccine response sub-study, 5ml of blood will be taken on the day of, and four weeks after receipt of the influenza vaccination, giving a total of no more than 10ml of blood collected.

Blood samples will be taken by the RN who, if needed, will have undergone geriatric phlebotomy training, or by a care home staff member if for example, they are already taking a blood sample for routine care, and/or the care home resident prefers this. The total volume of blood collected during the 6 to 12 month duration of the trial on any one participant will be no more than 36ml.

Each participant will be asked to provide a stool sample at baseline, three months and up to 12 months. The participants normal care provider will be asked to collect the stool samples.

Each participant will be asked to provide a saliva samples (saliva sample or oral rinse) at baseline, three months and up to 12 months.

If participants prefer not to provide any or all of the trial samples listed above this will not be a barrier to their entry to the PRINCESS trial.

All samples will be labelled with the participant unique trial identification number before being sent for analysis. Only fully trained and authorised members of the research team and laboratory staff will have access to the samples. The CI will ensure that the storage, analysis and disposal of all clinical samples will meet the requirements of the Human Tissue Act, 2004.

All tissue samples donated by trial participants will be taken on the understanding that they may be used for future research projects in the UK. The samples will be stored and subsequently distributed to approved projects in accordance with the Human Tissue Act and ethical legislation.

Any blood/saliva/stool test results will not be reported back to the CHR GP as they are being collected only for research purposes and will not be analysed in real-time.

#### **15.4 Follow-up**

The three and 6 to 12 month follow-up visit is detailed above in section 15.3.

## **16 Qualitative sub-study**

In addition to the main PRINCESS trial, a qualitative sub-study will be conducted after the end of data collection. The sub-study will consent PRINCESS trial participants, consultees, research nurses, care home staff and care home managers. The aim of the sub-study is to interview these groups of people about their involvement in the PRINCESS trial, and to examine how the PRINCESS research activities were carried out within the care home environment. The protocol for this sub-study can be found in Appendix 1.

### **16.1 Justification**

The set-up and the implementation of the PRINCESS trial was informed through past experience of other studies undertaken in care homes, as well as research around alternative models of consent (44-46). This qualitative study aims to examine how PRINCESS researchers, care home staff, and study participants worked to enact PRINCESS research activities.

The findings will inform the interpretation of the main study findings and also provide important information for those conducting research (including randomised controlled trials) in the care home context with practical recommendations and potential models of working with and within care homes. More specifically, the qualitative data will: provide a better understanding of the quantitative results, including reasons for missing data, and information about adherence to the study product; provide rich detail regarding how the PRINCESS consultee model of recruitment worked in practice; and what were the means (or barriers) by which PRINCESS researchers were able to recruit a representative cross section of those living in the care home.

## **16.2 Aims**

The overall aim of the study is to understand how the PRINCESS study was carried out within the care home context and identify the mechanisms which affected implementation of study activities.

## **16.3 Objectives**

The following objectives aim to be achieved:

1. Obtain research professionals' perspectives on the PRINCESS study, and gain an understanding of how they conducted the PRINCESS research activities within the care home.
2. Obtain care home staff perspectives on PRINCESS and the research activities associated with the study.
3. Obtain resident and consultee perspectives on PRINCESS and the research activities associated with the study.
4. Gain an understanding of the mechanisms which facilitated (or limited) conducting research activities in the care home.
5. Understand and gather contextual information that can assist the implementation of future research studies (including randomised controlled trials) with older people in care homes, a vastly under-researched setting.

## **16.4 Methods**

### ***Design***

Face-to-face or telephone semi-structured, qualitative interviews will be conducted with eligible participants - these are expected to take around 30 minutes. A topic guide will be developed which will be informed by relevant literature, and it will be piloted to ensure the interviews collect relevant data. Aspects of the research process of the RCT will be explored, with the aim to elucidate relevant contextual issues, barriers, and facilitators to the implementation of the RCT.

### ***Participant identification***

Participation will be limited to those who have already been involved in some capacity in the PRINCESS RCT. Ideally seven participants from each of the following groups will be interviewed:

1. PRINCESS RCT participants (care home residents) and family members/friends who a) acted as consultees for PRINCESS RCT participants who lacked capacity to provide informed consent or b) experienced/observed their relative/friend's participation in the PRINCESS RCT;
2. Managers of participating PRINCESS RCT care homes;
3. Care home staff that contributed to the research activities in the PRINCESS RCT;
4. Research professionals who conducted the research activities in the PRINCESS RCT.

### ***Recruitment***

The recruitment strategy will vary according to the potential participant group. Those within the care home environment (managers, staff, consultees and residents) will be 'snowball sampled'; i.e. managers will be approached initially. Managers can then approach staff, who in turn will then approach residents and consultees (47).

## **Consent**

All participants will be provided with an information sheet for the sub-study, and have the opportunity to ask questions and receive satisfactory responses, prior to the lead researcher seeking informed consent. Written informed consent will be obtained using a study-specific consent form prior to any data collection. A copy of the consent form will be provided to the participant, and the original retained by the lead researcher.

Participants will be informed that they are able to withdraw from the sub-study, should they wish to do so, by contacting the lead researcher. Data from participants who have withdrawn will not be used in the analysis. Participants are able to request to withdraw from the sub-study at any point, up until analysis is concluded.

## **Analysis**

The interviews will be digitally audio-recorded with consent and transcribed verbatim. All transcripts will be deidentified, and along with the source data will be stored confidentially on password protected servers maintained on the Cardiff University Network.

Data will be entered into Qualitative Data Analysis software (NVivo 11, QRS International) and iteratively coded using codes emerging from the data, and those identified *a priori*. Data will be analysed using framework analysis.

# **17 Statistical considerations**

## **17.1 Randomisation**

Participants will be individually randomised in a 1:1 ratio using minimisation. In order to achieve a balance of probiotic and placebo allocations within care homes, the care home from which a participant is recruited and gender of participant will be used as a minimisation variable. A random element, set at 80%, will be used in order to maintain the integrity of the minimisation process. The participants, treating clinicians, trial statistician and research nurses will remain unaware of the group to which participants are allocated during the trial. Pack IDs will be assigned probiotic / placebo allocations using randomly permuted blocks, and this list will be uploaded into the online system. This process will be carried out by a statistician independent of the trial team.

For more details, please consult the PRINCESS randomisation protocol.

## **17.2 Sample size**

### **Primary Outcome**

The original target for the PRINCESS trial was to randomise 330 participants from around 20 care homes in Wales and England. This would provide 90% power at the 5% level to demonstrate a 10% relative reduction in cumulative antibiotic administration days (CAAD) (assuming an average CAAD of 17.4 days and an absolute reduction in the probiotic arm to 15.6 days per resident-year). We consider that a 10% reduction is feasible and would be clinically important.

This sample size accounted for 30% of participants being lost to follow-up due to withdrawal or death during the study.

An interim assessment of primary outcome ascertainment revealed that the mean percentage of days for which there are valid antibiotic administration data (i.e. either no antibiotics administered, or the number of days antibiotics have been administered in a given week) is 77.4%, or 283 days out of a possible 365 on average. This percentage varies depending on the length of time participants have been in the study. However, it remains high for participants who have been in the study for over six-months, and does not take into account other data sources that might be used (e.g. hospital discharge summaries, medication administration records, etc.). This is likely to therefore reflect an underestimate of the availability of primary outcome data, but nevertheless is a more accurate reflection of the likely level of follow-up when compared to our original assumption.

Given slower than anticipated recruitment, and this new information regarding the trade-off between the number of participants required and average length of follow-up, we will aim to randomise between 258 and 270 participants. Assuming a mean number of days for which primary outcome data will be available (i.e. accounting for follow-up time and missing data) of approximately 250 days, this will provide at least 82% power to detect a 10% relative reduction in CAAD.

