### 3.3 Trial summary

Care home residents (CHR) are prescribed far more antibiotics than the general population because of the high burden of infections they bear, caused by weakened immunity, close-proximity living and multi morbidity (1). In our previous research in care homes, we found CHR took antibiotics for an average of 17.4 days per year (2). High antibiotic use increases the risk of reservoirs of antimicrobial resistance (AMR) in care homes that can spread within care homes and to hospitals and the community (1). This will intensify as the population ages. Infections in CHR cost the NHS >£54 M/year in hospitalisation alone (3) and infections are the commonest reason for CHR to be hospitalised. AMR infections are generally more serious and costly, particularly in older people. Reduction in antibiotic use and AMR could improve quality of life, save money, and help preserve the usefulness of existing antibiotics.

Other than vaccination and hygiene methods, there are few interventions proven to prevent infection in CHR. Probiotics are live bacteria that may confer health benefit by improving immune function and reducing carriage of potentially harmful bacteria. Probiotics are safe and cheap and are available as supplements. Probiotics may mediate positive changes in gut bacteria and therefore decrease immunity decline and infection. Reviews of studies found that probiotics reduced antibiotic use and risk of respiratory tract infections in adults (4) and reduced antibiotic associated diarrhoea (AAD) (5). Probiotics also reduced carriage of AMR bacteria in a review of critically ill patients, and have reduced duration of CID (6) and enhanced immune response, including to flu vaccination (7). However, research in CHR is currently lacking.

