#### **4.2 Rationale for current trial**

The 2010 Adult Social Care Statistics reported that there were 229,900 people in residential care in England, with numbers predicted to steadily increase. The 2011 census reported that there were 291,000 people over the age of 65 resident in the care home population in England and Wales (20). CHR are particularly prone to infections. The year-long observational study (n=274) identified 609 infections that led to an antibiotic prescription (incidence of 2.16 antibiotic prescriptions per resident year, 95% CI 1.90-2.46). The most common indications were RTI (47% of prescriptions), urinary tract infections UTI (29%) and skin infections (18%) (2). CID in CHR led to suffering, loss of dignity, hospitalisation, GP visits and death. Health needs assessment of 240 CHR in South Tyneside PCT identified 167 hospital admissions accounting for 1595 bed days over a year (21). On average, at least 4 beds in the Acute Trust are used for CHR all year round costing around £400K. About 25% of admissions were due to infection costing £100K in one PCT, or an estimated £54M/year for the UK. CIDs in CHR increase GP and care home burden and costs, impacting on opportunities for other aspects of care. Antibiotic prescribing leads to HCAIs such as *C. difficile* and drives AMR. The greatest risk of being infected with a AMR compared to a sensitive bacteria is recent consumption of antibiotics, even after controlling for age, comorbidity and other risk factors (22). AMR infections are more serious, last longer and are more costly to manage (23). Probiotics are effective in preventing AAD (5, 19), but we have no adequate data on prevention of all-cause common infections and antibiotic prescribing in care home residents.

There is an urgent need to reduce AMR through infection prevention in care homes. Urinary tract infections (UTIs) are usually caused by auto-inoculation; that is infection from our own bowel organisms. Carriage of AMR bowel organisms increases the chances of an AMR UTI. AMR Gram-negative septicaemia and AMR UTI are on the increase in the community, especially among older people (24). Care homes are a reservoir for AMR that cycle between the community and hospitals (3, 25). There is a steady increase in the care home population, and evidence-based interventions are needed to improve their quality of life through reducing the incidence of CIDs and antibiotic use (26).

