## **18 Analysis**

### **18.1 Main analysis**

The primary analysis will be by intention-to-treat, and will consist of a between-group comparison of the mean cumulative antibiotic administration days (CAAD) using Poisson regression. As the randomisation will be stratified by care home, the regression model will control for the care home a participant was recruited from. Negative binomial regression will be used in the presence of over-dispersed count data.

For secondary outcomes, depending on the type of data, a mixture of Poisson, linear, logistic and Cox models will be used to appropriately compare trial arms with respect to rates, means, proportions and time to events (see table below for more details).

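### The stated 90% and 82% power for a 10% reduction in CAAD hold only if antibiotic days have variance equal to their mean; the protocol's own figures suggest about 8 times that, and power of about 17-21%

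*Protocol*

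**What the plan says.** Protocol section 17.2 (Primary Outcome) makes two power statements about the same effect. For the original target of 330 participants with 30% loss: "This would provide 90% power at the 5% level to demonstrate a 10% relative reduction". The inputs given are means only: "assuming an average CAAD of 17.4 days and an absolute reduction in the probiotic arm to 15.6 days per resident-year". For the revised target of 258 to 270, with about 250 days of primary-outcome data per participant: "this will provide at least 82% power to detect a 10% relative reduction in CAAD". Neither statement gives a standard deviation, a dispersion parameter or an allowance for overdispersion. The section calls a 10% reduction feasible and clinically important.

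Elsewhere the protocol describes how antibiotic days arise. Section 3.3, citing reference 2: "we found CHR took antibiotics for an average of 17.4 days per year". Section 4.2, citing the same reference (n=274 over a year, 609 infections leading to a prescription): "incidence of 2.16 antibiotic prescriptions per resident year, 95% CI 1.90-2.46".

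On analysis, section 18.1 names Poisson regression and adds: "Negative binomial regression will be used in the presence of over-dispersed count data". The table in section 18.2 repeats this.

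**The concern.** Antibiotic days are not independent events; they come in courses. A resident given one more course gains about a week of antibiotic days at once. The variance of the yearly total must therefore exceed its mean unless something unusual offsets it, and the information in the trial is closer to a count of courses than to a count of days. The analysis section provides for overdispersion, but the power statement appears not to.

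At stake is what the trial can say about its primary question. The revised power was used to support lowering the target from 330 to 258-270. With 82% on record, a non-significant result could look more informative about a 10% effect than it is.

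**Working it through.** **Inputs.** Rates 17.4 against 15.6 days per resident-year (15.66 for an exact 10% cut), 5% level, 330 participants with 30% loss, 258-270 participants and 250 days (section 17.2); 1:1 allocation (section 17.1); 2.16 prescriptions per resident-year, CI 1.90-2.46, 609 events (section 4.2); 310 recruited (Appendix 1, Background). Sidedness is not stated; two-sided reproduces the figures.

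**Formula.** With n per arm, exposure t in years, mean days m1 = 17.4t and m2 = 15.6t or 15.66t, and dispersion φ = variance/mean:

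z = (m1 − m2) / √[φ(m1 + m2)/n], power = Φ(z − 1.96).

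The log-rate version agrees to within 0.1 point.

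**Step 1: reproduce the plan, φ = 1.**
- Original: n = 330 × 0.7 / 2 = 115.5, t = 1. With 15.66, z = 1.74/√(33.06/115.5) = 3.25 and power is 90.2%; with 15.6, 92.0%. Conversely, 90% power needs 115 per arm, and 230/0.7 ≈ 329, against 330 stated.
- Revised: t = 250/365 = 0.685. N=258 gives 81.2% (15.66) or 83.8% (15.6); N=270 gives 82.9% or 85.4%.

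So both powers, and the original N, match a calculation with variance equal to the mean.

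**Step 2: dispersion implied by sections 3.3 and 4.2.** Mean course length is 17.4/2.16 = 8.06 days. If the number of courses is Poisson and D is the length of a course, the total has variance/mean = E[D²]/E[D], which is at least E[D]. With equal course lengths the variance is 2.16 × 8.06² ≈ 140 against a mean of 17.4, so φ ≈ 8.06. Unequal course lengths or differing risk between residents raise it. Taking the CI limits for the rate, φ runs from 17.4/2.46 = 7.1 to 17.4/1.90 = 9.2.

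**Step 3: possible upper bound.** The quoted CI has log-scale SE ln(2.46/1.90)/3.92 = 0.0659. A Poisson count of 609 would have 1/√609 = 0.0405. The squared ratio is 2.64. If all of that excess is variation between residents, φ ≈ 8.06 × 2.64 = 21.3 over a year. At 250 days the factor is 1 + 1.64 × 0.685 = 2.13, and φ ≈ 17.

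**Step 4: power for a 10% reduction** (ranges cover 15.66 and 15.6).

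| φ | N=258, 250 days | N=270, 250 days | N=310, 250 days | Original (231 evaluable, 1 year) |
|---|---|---|---|---|
| 1 | 81-84% | 83-85% | 88-90% | 90-92% |
| 2 | 52-55% | 54-57% | 60-63% | 63-66% |
| 3 | 38-40% | 39-41% | 44-46% | 47-49% |
| 8.06 | 17-18% | 17-18% | 19-21% | 21-22% |
| 17 | 10-11% | 10-11% | 11-12% | 12-13% |
| 21.3 | 9% | 9-10% | 10% | 10-11% |

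Simulation with equal-length courses (20,000 runs, N=258, 250 days) gave 16.8% with Poisson courses and 11.0% with the extra between-resident variation.

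**Step 5: detectable reduction.** With 80% power at 250 days and φ = 8.06, it is about 27% at N=258 and 25% at N=310; at φ = 17, about 38% and 35%. For 82% power to detect a 10% cut at φ = 8.06, n per arm = (1.96 + 0.915)² × 8.06 × 33.06 / (0.685 × 1.74²) ≈ 1,062, or about 2,120 in total.

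**The case against.** **The figure of 8 is conditional.** The two reference-2 figures may not share a definition: section 3.3 gives no indication for the 17.4 days, so they could include long-term or non-infection use, while 2.16 counts prescriptions for infection. The denominators are also loose: 609/2.16 = 282 resident-years against n=274, although 609/274 = 2.22 changes φ only to 7.8. This stands, so a dispersion of at least 8 cannot be called established. It does not rescue the stated power: at N=258, φ = 7 gives 19-20%, φ = 5 gives 25-26% and φ = 2 gives 52-55%.

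**The upper end is weaker.** A reader might infer from the wide CI that true power is nearer 10%. The protocol does not say how that interval was computed. If care-home clustering widened it, that part largely drops out here, because allocation is balanced within care home and the model controls for care home. It can serve only as an unverified upper bound.

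**The analysis already provides for overdispersion.** True, and the validity of the test is not in question. But a negative binomial model corrects the standard error without restoring power, and adjusting for care home does not remove the clumping of days within a resident's courses.

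**Other inferences to avoid.** A reader might conclude that the trial could never detect a 10% reduction; power of 9-21% is low, not zero. Nor does any section propose reading a null result as excluding 10%. And the interim assessment in section 17.2 reports data completeness, not dispersion, so no dispersion estimate can be assumed to exist already.

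**Conclusion.** Wrong as written. The 90% and 82% are arithmetically correct for variance equal to the mean, an assumption that section 17.2 does not state and that the protocol's own description of antibiotic use contradicts. On the best reading of the protocol's figures, φ is about 8. Power for a 10% reduction is then about 17-19% at N=258-270, about 20% at 310 and about 21% for the original design, and the reduction detectable with 80% power is about 27% at N=258 or 25% at N=310. This rests on the 17.4 days and 2.16 prescriptions describing the same residents, and on course counts being at least as variable as Poisson. If the wide interval reflects differences between residents, φ could reach about 17-21 and power about 9-12%; that bound is unverified. That the stated power is well overstated does not depend on the exact φ, since even 2 or 3 leaves only about 52-55% or 38-40% at N=258.

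**What to change.** Restate section 17.2:

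- Say that 82% and 90% hold only if the variance of antibiotic days equals their mean.
- Give power and the detectable reduction under an explicit overdispersed (negative binomial) variance, over a range: about 8 as the main case, with about 17-21 labelled as an upper bound, and the assumptions behind each.
- Obtain a blinded pooled dispersion estimate from the collected data and use it to narrow the range.
- State that a non-significant result does not by itself exclude a 10% reduction.

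The cost is a rewritten paragraph and one blinded calculation, with a less favourable power figure on record. No extra recruitment and no change to the analysis model are needed.
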